Suicide has been described as "a permanent solution to a temporary problem" (3), reflecting the view that suicide is the result of poor decision making. The strongest biological finding in suicide research is the association with reduced serotonergic neurotransmission, particularly within the ventromedial prefrontal cortex (VMPFC) (4). This deficit in serotonergic neurotransmission is thought to impair cognition, predisposing patients to become more impulsive, rigid in their thinking, and poorer decision makers. Decisions during depressed states are tainted by negative affect and distorted negative cognitions (5). However, suicide has been associated with cognitive impairments that go beyond those of depression. Asymptomatic patients with a history of suicide attempts exhibit significant cognitive deficits suggestive of generalized prefrontal cortex (PFC) dysfunction (6, 7), and corollary disruptions in risk assessment (8). Poor inhibition is found in suicide attempters when compared with patients with only suicidal ideation (9), and greater cognitive impairments are found in depressed patients with suicidal ideation compared to those without it (10). It is possible that cognitive deficits may be specific to suicidal behavior rather than to any comorbid or specific psychiatric diagnosis because this observation holds true for suicidal patients with depression, bipolar disorder, and even temporal lobe epilepsy. However, most of these studies were performed in symptom-free patients, often months or years after the presence of suicidal ideation or behavior. In a previous report (1) we demonstrated that inability to delay gratification (choosing smaller immediate rewards over larger delayed rewards) is shared by both recent suicide attempters and depressed patients with suicidal ideation. On a follow up assessment, 5-10 days after the suicide attempt, reduction of suicidal ideation and intent was correlated with decreased symptoms of depression

and recovery of delayed gratification impairments (1). These data are congruent with the hypothesis that stressful situations in combination with a biological and psychological predisposition may create a critical climate of overwhelming psychological pain in an individual who chooses an impulsive escapist strategy to terminate his/her own life discounting all future outcomes (11). However, the underlying neural mechanisms remain unknown and therefore not amenable to therapeutic interventions.

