SA1. Determine the safety of repetitive transcranial magnetic stimulation (rTMS) in depressed patients with severe suicidal ideation.

Hypothesis 1: Given studies of rTMS for clinical depression, we predict that rTMS in patients with severe suicidal ideation will be well tolerated and not associated with significant side effects.

SA2. Determine the effect of rTMS on delay discounting on depressed patients with severe suicidal ideation.

Hypothesis 2: In depressed patients with severe suicidal ideation the rTMS active will reduce impulsive choice behavior (measured as delay discounting) compared with the non-treatment group

SA3. Determine the effect of rTMS on suicidal ideation on depressed patients with severe suicidal ideation.

Hypothesis 3.1: In depressed patients who had recently attempt suicide the rTMS active group will reduce suicidal ideation severity (measured by the Beck Scale for Suicidal Ideation) compared with the non-treatment group

Hypothesis 3.2: Suicidal ideation in depressed patients who recently attempt suicide will vary in function of

PI: [name] delay discounting.

SA4. Identification of biomarkers of positive response to rTMS in depressed patients with severe suicidal ideation.

Hypothesis 4: A composite of serum hormonal and inflammatory markers will predict positive response to rTMS in depressed patients with severe suicidal ideation.

Significance

Achieving the goals of this proposal will provide understanding of the neurobiological mechanisms of suicidality and proof of concept for the use of rTMS as adjunctive treatment for acute suicidality. This new knowledge would lead prospective studies testing the clinical value of rTMS to improve impulsive choice behavior to reduce suicide behavior in persons at high risk.

STUDY DESIGN AND PROCEDURES

Experimental design

A double blinded randomized controlled trial with assignment to active rTMS experimental treatments or sham will recruit adult patients (18-60 years old) of both genders voluntarily admitted to the PRI inpatient units following a recent suicide attempt with persistent suicidal ideation or because of severe suicidal ideation.

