The Principal Investigator will carefully monitor study procedures to protect the safety of research subjects, the quality of the data and the integrity of the study. To protect the identity of research volunteers, contact information will be stored in a separate file and locked cabinet, away from experimental data forms. All study subject material will be assigned a unique identifying code or number. The key to the code will be kept in a locked file in the Study Coordinator's office. Only [name] and designated research staff will have access to the code and information that identifies the subject in this study. All experimental data will be identified using a study code rather than a name, social security number, or other identifying information. All data collection forms will be kept in a locked cabinet in the Psychiatric Research Institute. Computer data records will remain on UAMS maintained password protected network drives.

DATA ANALYSIS

Cognitive tests and questionnaires

Data will be scored and analyzed/summarized according to instructions. Scores will be analyzed via t-tests, analysis of variance (ANOVA) or regression analysis.

PI: [name]

The primary outcome (impulsive choice measured by delay discounting) will be analyzed using an MMRM (mixed model repeated measures) approach based on a modified intent-to-treat (mITT) population. The mITT population will be defined as randomized subjects who started at least one treatment. Participants from the mITT population who are included in the MMRM model will also require both a baseline and at least one post- baseline SSI score. The model will include as the dependent variable change from baseline in delay discounting indifference point (K) at each post-baseline visit during the acute phase. Independent variables in the MMRM model will include treatment, visit, treatment-by-visit interaction, delay discounting at baseline, gender, age at baseline and diagnosis. Visits (Days 0, 1, 2, 3) will be treated as a categorical variable. Unstructured variance-covariance structure will be used. This same analysis will also be repeated on the completers' population, defined as subjects who completed 3 days of treatment with the scheduled maximum 6000 pulses per session.

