Analyses of VAS data will be conducted using a similar MMRM approach. Each VAS item will be analyzed separately. For the suicide, mood and anxiety items, the model included as the dependent variable change scores from pre-session 1 (session prior to intervention) to each post-session (sessions 1-9) during the acute phase. Independent variables included treatment, session, treatment-by-session interaction, VAS score at pre-session 1, gender, age at baseline, and diagnosis. Painfulness questions collected only at each post-session will be analyzed using an MMRM approach with post-session scores as the dependent variable. Independent variables will remain the same.

Descriptive analyses will be performed to compare baseline data between treatment groups. Categorical variables will be evaluated using Fisher's exact test. Continuous variables will be analyzed with Wilcoxon's rank sum test.

Safety data will be summarized overall and by treatment groups. Fisher's exact test will be used to compare the number of subjects between groups who experienced any adverse events. Length of hospital stay will be compared using Wilcoxon Rank Sum test. Time to re-admission will be analyzed with log-rank test.

The Stroop Test, N-Back scores and pain pressure threshold will be added as covariates in final analysis. Other secondary efficacy outcomes (HRSD, MADRS, CAPS and SSI) for the extended safety phase will be analyzed with MMRM model. The model will include the change from baseline at each follow-up visit as the dependent variable. Independent variables include treatment, visit, treatment-by-visit interaction and base- line score.

We will use repeated measures ANOVA (with appropriate statistical corrections) to compare measures obtained at baseline to those collected 3 & 6 months after all experimental treatment ends. This analysis will address long-term effects of rTMS experimental treatment on suicidal ideation.

The integrity of the blind will be analyzed by tables and Fisher's exact test.

All statistical analyses will be performed in R version 2.14.0. Because this is an early phase study, no adjustments will be made for multiple comparisons, and a *P*-value of 0.05 will be considered to be statistically significant.

Power estimation

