Based on our previous results, we consider a meaningful clinical difference as one equal to or higher than that found between recent suicide attempters with persistent suicidal ideation (delay discounting rate (K)=0.122) compared to depressed patients with active suicidal ideation (K=0.099), thus d=0.23 (1).

Given these effect sizes, we determined that a sample of 10 experimental treatment responders will yield power of .80 or greater to detect change in tinnitus. We expect that the sample size proposed for this pilot study, 20 subjects, is sufficient to test our hypothesis as planned.

PI: [name]

ETHICAL CONSIDERATIONS

This study will be conducted in accordance with all applicable government regulations and University of Arkansas for Medical Sciences research policies and procedures. This protocol and any amendments will be submitted and approved by the UAMS Institutional Review Board (IRB) to conduct the study. Given the transient state (severe acute suicidal ideation) targeted in this study, the earliest assessment of these patients is crucial in order to obtain a glimpse of the state of mind of the individual that led to engage in suicidal behavior or to ask for help in order to prevent doing so.

Vulnerable population: An ethical concern is that some patients may be receiving medical care involuntarily, and thus represent a vulnerable population with compromised ability to provide informed consent. Thus, no involuntary patients will be recruited in this study. We have ongoing projects [UAMS IRB#139056] and have executed successfully previously similar studies [University of Miami IRB# 20110619] with acutely suicidal patients in collaboration with IRB panels. Additionally, even though these patients have recently attempted suicide or are acutely suicidal, the fact that they would be hospitalized provides an additional layer of protection to this vulnerable population. We will work closely with the IRB to assure that all ethical concerns are addressed.

STUDY REGISTRATION AND PUBLICATION

The PI, Co-Is, and associates are active researchers and publish in a variety of academic journals. It is anticipated that results from this study will be published in similar academic journals. All manuscripts published in peer-reviewed journals will be made publicly available in PubMed Central as per the requirements for studies supported by NIH funding.

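### The claim of at least 0.80 power rests on d=0.23, whose standardiser is not stated and is not tied to change in K; at face value it gives about 8% with 10 per arm

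*Combined protocol and SAP*

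**What the plan says.** Under DATA ANALYSIS, Power estimation, the plan takes as its meaningful difference the gap in delay discounting rate between two patient groups in the team's earlier study: "recent suicide attempters with persistent suicidal ideation (delay discounting rate (K)=0.122") "compared to depressed patients with active suicidal ideation (K=0.099), thus d=0.23 (1"). No SD, variance or group size accompanies the two values, and none for K appears elsewhere in the document.

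The next sentence draws the conclusion: "a sample of 10 experimental treatment responders will yield power of .80 or greater to detect change in tinnitus". The section then says that the pilot sample of 20 is enough to test the hypothesis as planned.

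The quantity to be analysed is defined earlier under DATA ANALYSIS (Cognitive tests and questionnaires). Delay discounting is called the primary outcome, and the MMRM's dependent variable is "change from baseline in delay discounting indifference point (K) at each post-baseline visit during the acute phase", with treatment, visit, their interaction and baseline delay discounting among the model terms. Hypothesis 2 is a between-group statement: active rTMS "will reduce impulsive choice behavior (measured as delay discounting) compared with the non-treatment group". STUDY POPULATION gives a target of 20 randomised 1:1, so 10 per arm. On the significance level, the plan says that a P-"value of 0.05 will be considered to be statistically significant"; sidedness is not given.

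**The concern.** A standardised effect size does not follow from two means alone, yet the text presents d as a consequence of the two K values. The reader cannot tell what 0.23 was divided by. Whatever the divisor, the comparison is cross-sectional and between two kinds of patient. The planned test concerns change in K over the treatment days, compared between randomised arms and adjusted for baseline K. The SD that matters there depends on how strongly baseline and later K are correlated, and the plan states neither that SD nor the correlation.

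At stake is the one quantitative claim about what the trial can detect. If power is far below 0.80, a null result on delay discounting would say very little, but a reader who trusted the stated figure would take it as evidence against the hypothesis. The mention of tinnitus and of responders adds to the doubt that the figure was worked out for this endpoint.

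**Working it through.** **Inputs.** From Power estimation: K = 0.122 and 0.099, d = 0.23, power at least 0.80. From STUDY POPULATION: 20 subjects, 1:1, so 10 per arm. From DATA ANALYSIS: alpha 0.05, taken here as two-sided, with one-sided also checked. SDs and baseline-to-follow-up correlations (rho) are not in the documents; every value used below is an assumption. Power is from the noncentral t for a two-sample comparison at one visit, a simplification of the MMRM.

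**Step 1: where 0.23 could come from.** The difference is 0.122 − 0.099 = 0.023.
- Divided by 0.099: 0.232. Divided by 0.122: 0.189. Divided by the average, 0.1105: 0.208.
- As a Cohen's d: SD = 0.023/0.23 = 0.100 (0.098 to 0.102 allowing for rounding).

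So 0.23 matches the relative difference on the 0.099 base, and equally a Cohen's d with an SD of about 0.10.

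**Step 2: try to reproduce 0.80 from d = 0.23.** Noncentrality = 0.23 × √(10/2) = 0.514.
- 10 per arm: 7.8% two-sided, 12.5% one-sided.
- 14 per arm (all 28 recruits analysed): 9.0% two-sided.
- One-sample or paired test, n = 10, in case the 10 responders were meant that way: 10.0% two-sided, 16.6% one-sided.
- Paired, n = 20: 16.5% two-sided, 25.7% one-sided.

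No variant reaches 0.80. The number per arm for 80%, two-sided, is 2 × (1.960 + 0.842)²/0.23² ≈ 297 by the normal formula and 298 by the t. With 10 per arm, 80% power needs d ≈ 1.32, that is SD = 0.023/1.325 ≈ 0.0174.

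**Step 3: if 0.23 is a Cohen's d on single-time K.** With equal variances at the two times, the baseline-adjusted effect size is 0.23/√(1 − rho²).

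| Assumed rho | Adjusted d | Power, 10 per arm |
|---|---|---|
| 0.5 | 0.266 | 8.7% |
| 0.7 | 0.322 | 10.5% |
| 0.8 | 0.383 | 12.8% |
| 0.9 | 0.528 | 20.1% |
| 0.95 | 0.737 | 34.5% |

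Reaching 80% needs rho ≈ 0.985.

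**Step 4: if 0.23 is a relative difference.** Only the raw 0.023 is then known, and d = 0.023/SD for an assumed SD of the analysed variable.

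| Assumed SD | d | Power, 10 per arm |
|---|---|---|
| 0.02 | 1.15 | 68% |
| 0.03 | 0.77 | 37% |
| 0.05 | 0.46 | 16% |
| 0.10 | 0.23 | 8% |
| 0.20 | 0.12 | 6% |

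**Step 5: precision.** The 95% half-width for the between-arm difference is t(18 df) × SD × √(2/10) = 2.101 × 0.447 × SD = 0.94 × SD. With an assumed single-time SD of 0.10, the adjusted SDs at rho 0.5, 0.7 and 0.9 are 0.087, 0.071 and 0.044. The half-widths are 0.081, 0.067 and 0.041, all wider than the target of 0.023.

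**The case against.** The strongest reply is that 0.23 is labelled d and cited to the team's own published study. A protocol may quote a published effect size without reprinting its SD. The match to the relative difference is weak evidence: several denominators were tried, one fits, and because the base mean is itself close to 0.10, a true SD of about 0.10 gives the same number. This stands. A reader might infer that 0.23 is shown to be a percentage difference mislabelled as d; the documents do not support that, and no arithmetic slip in 0.23 itself is demonstrated.

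A reader might also infer that d=0.23 can support no power figure at all. That goes too far. A Cohen's d on single-time K becomes usable once a correlation is assumed, as Step 3 shows. Under the equal-variance formula, leaving the correlation out understates power.

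It can also be said that 0.80 was perhaps never derived from 0.23. The section writes "Given these effect sizes, we determined that a sample of 10 experimental treatment responders" in the plural although it prints only one, and it names tinnitus and responders, which may mean the sentence was written for another study. That is possible, but it does not rescue the claim: the figure is then unsupported for this trial rather than miscalculated.

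Finally, the trial is described as a pilot, and the background section names safety as the primary objective. This lowers the stakes. It does not excuse the statement, since DATA ANALYSIS calls delay discounting the primary outcome and the power paragraph asserts that the sample is enough to test the hypothesis.

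**Conclusion.** The point holds. The stated power of at least 0.80 is not delivered by the only effect size printed. At face value d=0.23 gives about 8% with 10 per arm, and no more than 26% under the most favourable face-value variant tried (one-sided, paired, n = 20). The standardiser behind 0.23 is not stated. Under either reading of the figure, nothing ties it to the SD of baseline-adjusted change in K.

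The size of the true shortfall cannot be fixed from the documents. It is 6% to 37% power for assumed SDs of 0.20 down to 0.03, or about 9% to 20% for assumed correlations of 0.5 to 0.9 if 0.23 is a Cohen's d. Power of 0.80 would require an SD near 0.0174 or a correlation near 0.985, and the plan offers nothing in support of either. The one-visit two-sample approximation leaves out the other covariates and any gain from combining visits.

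The paragraph should be corrected. Given the pilot purpose, this is not a reason to change the design.

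**What to change.** Rewrite the Power estimation paragraph:

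- Keep the raw target of 0.023 in K, and say whether 0.23 is a Cohen's d or a relative difference.
- State the SD used and its source, and give power for the active-versus-sham difference in change in K at 10 per arm.
- Withdraw the claim of at least 0.80 power and the statement that 20 subjects suffice to test the hypothesis. Print instead the recomputed power (about 8% at d=0.23) or the expected 95% half-width.
- Remove the references to tinnitus and to treatment responders.
- Look to the earlier study for the SD of change and the baseline-to-follow-up correlation. BACKGROUND AND RATIONALE shows that patients were re-assessed: "On a follow up assessment, 5-10 days after the suicide attempt, reduction of suicidal ideation and intent was correlated with decreased symptoms of depression". It reports neither quantity, so they should not be assumed to be in hand, and 5-10 days only approximates the 3-day treatment course. If the correlation cannot be recovered, show results at assumed values of 0.5, 0.7 and 0.9.

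The cost is one paragraph and a short calculation, with no extra patients or procedures. The downside is a much less favourable stated figure.

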Delay discounting task	X	X	X	X	X	X			
N back test	X	X	X	X	X	X			
Stroop Test	X	X	X	X	X	X			
Young Mania Rating Scale	X	X	X	X	X	X			
DKEFS Verbal Fluency Test	X	X	X	X	X	X			
Pressure pain threshold	X	X	X	X	X	X			
Sham validating measure				X					
Trail making A and B	X	X	X	X	X	X			
Visual Analog Scales**	X	X	X	X	X	X			
MINI International	X								
Neuropsychiatric Interview (MINI)									
Randomization	X								

^{**} This assessment will be collected 3 times per day pre and post rTMS.

Safety Assessments

Research staff will use the MedDRA System Organ Class (SOC) and preferred term (PT) to document adverse events, which will be assessed at each treatment, and at follow-up visits.

This protocol will not modify patient care and our visits will not interfere with regular clinical care, except in the case of imminent danger to the patient or others in which appropriate measures will be taken, like contacting the primary treatment team and placing the patient on 1:1 observation until evaluation by the primary team.

STUDY POPULATION

Participant recruitment will occur at the inpatient units at the Psychiatric Research Institute (PRI). Target sample size is 20, which will be randomized into active or sham groups (1:1). Considering 40% attrition rate we plan to recruit 28 participants.

Recruitment: Recruitment will be facilitated by the PI's role of PRI inpatient attending physician. The success of this proposal depends heavily on the ability to recruit patients very soon after hospitalization for

PI: [name]

suicide ideation or behavior.

All participants will be compensated \$40 for their participation in each of the 3 rTMS sessions of the active phase of the study and the 2 follow-up sessions. Participants can earn a total of \$200 for completing the entire study, including both follow up visits.

Inclusion Criteria

- a) Age 18-60 years, of all races and ethnicities;
- b) Admitted voluntarily to the adult psychiatric inpatient at PRI;
- c) Suffering from a current depressive episode as defined by the DSM-V
- d) Currently have diagnoses of major depressive disorder
- e) Reason for hospitalization should be a recent suicide attempt or suicidal ideation
- f) Current severe suicidal ideation defined by a score >7 in the Beck Scale for Suicidal Ideation
- g) Must pass the TMS safety checklist (TASS)
- h) Women of childbearing age must have a negative result on a pregnancy test
- i) Ability to read, write and speak English.

Exclusion Criteria

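### At the plan's own effect size of d=0.23, 10 subjects per arm give about 8% power, not .80, and the power sentence is about tinnitus, which this trial does not measure

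*Combined protocol and SAP*

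**What the plan says.** The Power estimation section, at the end of Data Analysis, compares the mean discounting rate K in recent suicide attempters (0.122) with that in "depressed patients with active suicidal ideation (K=0.099), thus d=0.23", and takes this as the smallest clinically meaningful difference. The next sentence, introduced as following from these effect sizes, says that "a sample of 10 experimental treatment responders will yield power of .80 or greater to detect change in tinnitus". The section ends by stating that "the sample size proposed for this pilot study, 20 subjects, is sufficient to test our hypothesis as planned".

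The hypothesis in question is Hypothesis 2 under SA2: "the rTMS active will reduce impulsive choice behavior (measured as delay discounting) compared with the non-treatment group". Study Population sets the target at 20 subjects, randomised 1:1 to active or sham, with 28 to be recruited to allow for 40% attrition. Data Analysis states: "The primary outcome (impulsive choice measured by delay discounting) will be analyzed using an MMRM". The model takes change from baseline in K as the dependent variable and adjusts for baseline K, gender, age and diagnosis; "Visits (Days 0, 1, 2, 3) will be treated as a categorical variable". There is no multiplicity adjustment, and a P-value of "0.05 will be considered to be statistically significant". Sidedness is not stated. The plan gives no SD for K and no correlation between visits.

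**The concern.** Two things are wrong in the one sentence that carries the sample size.

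First, it describes a different study. Tinnitus is in no aim or hypothesis and in neither assessment table; elsewhere it appears only as earlier rTMS work and in the discussion of risks. A group of responders is defined after treatment and is not a randomised arm. The sentence therefore supports no comparison that this trial will make.

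Second, an effect of d=0.23 is small, and 10 per arm cannot give 80% power for it with any ordinary test.

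This paragraph is the plan's only statistical reason for 20 subjects. If rTMS produced exactly the difference the plan calls meaningful, an unadjusted comparison would still miss significance about 9 times in 10. A reader who trusts the stated .80 would take a non-significant result as fair evidence that rTMS does not alter impulsive choice, when the result would say very little either way.

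**Working it through.** **Inputs from the plan.** d=0.23 and the two K values (Power estimation); 20 subjects, 1:1, so 10 per arm (Study Population); alpha 0.05 (Data Analysis). Figures are two-sided unless stated and use the noncentral t distribution.

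**1. Effect size.** The difference in K is 0.122 − 0.099 = 0.023. If d is the mean difference divided by the SD, the implied SD is 0.023/0.23 = 0.10.

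**2. The plan's figure, for the planned comparison.** The noncentrality is d × √(n/2) = 0.23 × √5 = 0.514, with 18 df and a critical value of 2.101. Power is **7.8%** two-sided and **12.5%** one-sided. The stated figure is .80 or greater. It is not reproduced.

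**3. The literal one-group reading.** For change in 10 treated subjects, with d in SDs of change, the noncentrality is 0.23 × √10 = 0.727 with 9 df. Power is 10.0% two-sided and 16.6% one-sided. With d in between-subject SDs, the standardised change is d/√(2(1−r)); power is 10%, 13% and 31% at r = 0.5, 0.7 and 0.9. This does not reproduce .80 either.

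**4. Credit for baseline adjustment and repeated visits.** Assume equal correlation r between all visits (compound symmetry). The mean of k post-baseline visits, adjusted for baseline, then has a residual variance factor of (1+(k−1)r)/k − r², which is 1 − r² for one visit. Divide d by the square root of that factor and use 17 df. The values of k are 1; 3 (days 1 to 3); 5 (the acute post-baseline delay discounting assessments in Table 2); and 6 (adding the pre-discharge assessment).

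| Visits averaged | r=0.5 | r=0.7 | r=0.9 | r needed for 80% |
|---|---|---|---|---|
| 1 | 8.7% | 10.5% | 20.0% | 0.985 |
| 3 | 11.7% | 14.1% | 28.2% | 0.977 |
| 5 | 13.0% | 15.5% | 31.0% | 0.975 |
| 6 | 13.4% | 15.9% | 31.8% | 0.974 |

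Fitting gender, age and diagnosis as well (14 df) lowers the r=0.9 figures slightly, to 27.6% for 3 visits and 31.2% for 6.

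**5. If all 28 recruits were analysed.** With 14 per arm, power is 9.0% unadjusted. Averaging 3 to 6 visits gives 15% (3 visits, r=0.5) to 43% (6 visits, r=0.9). This is generous, because the plan itself expects 40% attrition.

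**6. What 10 per arm can detect.** Power of 80% needs d = 1.32 unadjusted. At an SD of 0.10 that is a K difference of 1.32 × 0.10 ≈ 0.13 (0.12 to 0.14 allowing for rounding in the plan's figures), against a highest cited mean K of 0.122. For d=0.23, 80% power needs 298 per arm (235 one-sided).

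**7. Precision.** The expected 95% CI half-width, unadjusted, is 2.101 × √(2/10) = 0.94 SD, and 0.94/0.23 ≈ 4, so about four times the difference of interest.

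**The case against.** **It is a pilot, and safety comes first.** The Background section names safety as the primary objective and endpoint, SA1 is safety, and the plan calls itself early phase and a pilot. A pilot need not be powered for efficacy, and poor power for SA2 does not undermine the safety aim. That stands, and it is why no larger sample is asked for. It does not excuse an explicit .80 claim for what Data Analysis calls the primary outcome, judged against a significance threshold.

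**The .80 may belong to another calculation.** The sentence speaks of change, responders, tinnitus and effect sizes in the plural, so it may be carried over from a tinnitus study with its own effect size lost. That is plausible. The defect would then be a missing calculation rather than a miscalculated one. As written, though, the sentence ties itself to d=0.23, and under either account the plan has no valid power statement for delay discounting.

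**The ceiling of 32% depends on stopping at r=0.9.** This is fair, since the documents give no correlation. At r=0.95, two-sided power with 10 per arm runs from 34% (1 visit) to 54% (6 visits). With all 28 analysed, 6 visits and r=0.95, it is 70% two-sided and about 80% one-sided. Reaching .80 takes all of those favourable conditions at once, or a correlation of about 0.974 or higher.

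**Averaging visits is not the stated test.** Correct. The plan fits treatment by visit with unstructured covariance and does not say which contrast is tested; the pre-discharge assessment is outside its Days 0 to 3. The multi-visit figures show how far the planned model could help, and are not exact power for it.

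**Conclusion.** The concern holds and must be fixed. At the plan's own d=0.23 with 10 per arm, power is 7.8% two-sided (12.5% one-sided) before adjustment, roughly a tenth of what is claimed. This rests only on the plan's figures and a standard two-sample t test.

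Allowance for baseline adjustment and up to six averaged visits brings the two-sided figure to between about 9% and 32%. That range assumes correlations of 0.5 to 0.9 and compound symmetry, neither of which is in the plan. A true effect of the stated size would therefore miss p<0.05 about 7 to 9 times in 10 even with that help. The outcome named in the power sentence is not measured in this trial.

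**What to change.** Replace the power paragraph. Remove the references to tinnitus and responders and the statement that 20 subjects suffice to test the hypothesis. Suggested text:

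> With 10 subjects per arm, power to detect d=0.23 in delay discounting is about 8% (two-sided alpha 0.05, unadjusted). With baseline adjustment it is about 9–20% for one visit, and about 12–32% when 3 to 6 post-baseline assessments are averaged, for assumed correlations of 0.5–0.9 and compound symmetry. Power of 80% is reached only for d of about 1.3 (unadjusted). The delay discounting result will be read from its estimate and 95% CI (expected half-width about 0.94 SD, unadjusted), and a non-significant result will not be read as absence of effect.

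If a one-sided test is meant, say so and give 12.5% as the unadjusted figure. Because the old paragraph was the only statistical reason for 20 subjects, it would help to add the real one, such as safety or feasibility, but the correction is sound without it.

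The cost is protocol wording and a much less favourable power figure. No patients, visits or analyses are added and the planned model is unchanged; what changes is how a non-significant result is read.
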